7.8.2.3. Management of Patients with Severe, Persistent Hyperglycemia during the Treatment Period

Severe, persistent hyperglycemia will be collected during the trial to assess the risk of extreme imbalance in glycemic control.

Investigators will be trained on the application of criteria for deciding when and how to intervene with patients who do not reach glycemic targets. If any of the FBG values within 1 week for 2 consecutive weeks exceed the limits outlined below and no intercurrent cause of the hyperglycemia could be identified (investigators should first confirm that the patient is fully compliant with the assigned therapeutic regimen and that he or she does not have an acute condition causing severe hyperglycemia), rescue medication will be prescribed as an add-on to randomized treatment. Patients will continue to follow the protocol-specified visit schedule as described in Section 7.4.2.

- >270 mg/dL (>15.0 mmol/L) from baseline to Week 6 (4 values/week)
- >240 mg/dL (>13.3 mmol/L) from Week 6 to Week 12 (4 values/week)
- >200 mg/dL (>11.1 mmol/L) from Week 12 to end of trial (4 values/week)
OR
- HbA1c \geq 8.5% (\geq 69 mmol/mol) by and after Week 24

7.8.2.4. Management of Patients Permanently Discontinuing Study Drugs

Circumstances under which patients may be required to prematurely discontinue study drug are outlined in Section 8.1. Patients who stop the study drug permanently will continue participating in the trial according to the protocol to collect all planned efficacy and safety measurements and should receive another glucose-lowering intervention (Section 7.4.2). The new glucose-lowering intervention will be recorded on the eCRF specified for collecting antihyperglycemic medications.

To assure timely initiation of another antihyperglycemic medication after permanent discontinuation of study drug, patients should be advised to promptly notify the site when this

situation occurs. The investigator should evaluate the need for additional antihyperglycemic medication at this time (as outlined in Section 7.4.2) and initiate the additional intervention accordingly. An unscheduled visit should be used as needed for more timely initiation if warranted based on the investigator's clinical judgment.

7.8.2.5. Management of Patients with Gastrointestinal Symptoms

In the Phase 2 program, the most commonly reported treatment-emergent AEs (TEAEs) for patients receiving tirzepatide were nausea, vomiting, and diarrhea.

The tirzepatide dose escalation scheme has been designed to minimize the development of intolerable GI symptoms. The escalation period is considered to be 24 weeks, which allows 20 weeks to escalate to 15 mg and additional 4 weeks to reach steady state. During the dose escalation period, every effort should be made by the investigator to be able to escalate and maintain patients on the corresponding study drug dosage.

To mitigate GI symptoms and manage patients with intolerable GI AEs during the escalation period (Week 0 to 24), the investigator should

- advise patients to eat smaller meals, for example, splitting 3 daily meals into 4 or more smaller meals, and to stop eating when they feel full.
- prescribe symptomatic medication (for example, antiemetic or antidiarrheal medication) per local country availability and individual patient needs. Use of symptomatic medication should be captured as concomitant medication in the eCRF.
- temporarily interrupt tirzepatide (omit 1 dose, the patient will take 3 of 4 doses at that dose level). After the interruption, restart at the same dose with the patient taking medication to alleviate their GI symptoms. The data related to temporary interruption of study treatment should be documented in source documents and entered on the eCRF.
- If intolerable GI symptoms or events persist despite the above measures, the investigator may decide to discontinue study drugs. De-escalation of study drugs will not be allowed. Patients who stop the study drug permanently will receive another glucose-lowering intervention (Section 7.4.2) and will continue participating in the study according to the protocol to collect all planned efficacy and safety measurements. The new glucose-lowering intervention will be recorded on the eCRF specified for collecting antihyperglycemic medications.

In the event of intolerable persistent GI symptoms that occur after the escalation period (after Week 24), the investigator should take the above measures to keep the patient on study treatment before stopping the study drug permanently and initiate another glucose-lowering intervention.

8. Discontinuation Criteria

8.1. Discontinuation from Study Treatment

8.1.1. Permanent Discontinuation from Study Treatment

Possible reasons leading to permanent discontinuation of investigational product:

- **Patient Decision**
 - The patient requests to discontinue investigational product.
- **Discontinuation due to increased risk of hypoglycemia**
Please refer to Section [7.8.2.2](#) for details.
- **Discontinuation due to a hepatic event or liver test abnormality**

Patients who are discontinued from investigational product due to a hepatic event or liver test abnormality should have additional hepatic safety data collected via an eCRF.

Discontinuation of the investigational product for abnormal liver tests **should be** considered by the investigator when a patient meets one of the following conditions after consultation with the Lilly-designated medical monitor:

- ALT or aspartate aminotransferase (AST) >8X ULN
- ALT or AST >5X ULN for more than 2 weeks
- ALT or AST >3X ULN and total bilirubin level (TBL) >2X ULN or international normalized ratio >1.5
- ALT or AST >3X ULN with the appearance of fatigue, nausea, vomiting, right upper quadrant pain or tenderness, fever, rash, and/or eosinophilia (>5%)
- alkaline phosphatase (ALP) >3X ULN
- ALP >2.5X ULN and TBL >2X ULN
- ALP >2.5X ULN with the appearance of fatigue, nausea, vomiting, right quadrant pain or tenderness, fever, rash, and/or eosinophilia (>5%)

In addition, patients will be discontinued from the investigational product in the following circumstances:

- If a patient is inadvertently enrolled and it is determined that continued treatment with study drug would not be medically appropriate, see Section [8.1.3](#)
- Acute or chronic pancreatitis
- If a patient is diagnosed with MTC after randomization or has a postrandomization calcitonin value ≥ 35 ng/L that has increased at least 50% over baseline
- If a patient is diagnosed with an active or untreated malignancy (other than basal or squamous cell skin cancer, in situ carcinomas of the cervix, or in situ prostate cancer) after randomization

- Any significant study drug-related hypersensitivity reaction
- Any other TEAE, SAE, or clinically significant laboratory value for which the investigator believes that permanent study drug discontinuation is the appropriate measure to be taken
- If female patient becomes pregnant
- If a patient is diagnosed with T1DM

Patients who stop the study drug permanently will receive another glucose-lowering intervention and will continue participating in the trial according to the protocol to collect all planned efficacy and safety measurements. The new glucose-lowering intervention will be recorded on the eCRF specified for collecting antihyperglycemic medications.

Patients discontinuing from the investigational product prematurely for any reason should complete adverse event and other follow-up procedures per Section 2 (Schedule of Activities), Section 9.2 (Adverse Events), and Section 9.4 (Safety) of this protocol.

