Abbreviations: ADA = anti-drug antibody; APPADL = Ability to Perform Physical Activities of Daily Living; BG = blood glucose; BP = blood pressure; CKD-EPI = Chronic Kidney Disease-Epidemiology; ECG = electrocardiogram; eCRF = electronic case report form; eGFR = estimated glomerular filtration rate; EQ-5D-5L = European Quality of Life-dimensions; ET = early termination; F/U= follow-up; HbA1c = hemoglobin A1c; HR = heart rate; IW-SP = Impact of Weight on Self-Perception; PK = pharmacokinetics; PRO = patient-reported outcome; SMBG = self-monitoring of blood glucose; Tx = treatment.

- a Baseline assessments must be completed before processing in the interactive web-response system (IWRS).
- b Patients who are unable or unwilling to continue in the study for any reason will perform an ET visit. If the patient is discontinuing during an unscheduled visit, that visit should be performed as the ET visit. If the patient is discontinuing during a scheduled visit, that visit should be performed as an ET visit. Visit 801 (safety follow-up visit) should be performed 4 weeks after the ET visit as the final study visit.
- c The visit date is determined in relation to the date of the randomization visit (\pm the allowed visit window).
- d On visits 3, 4, 6, 7, 9, 10, 12, 13, 14, ET, and at follow-up, patients should be reminded to report to the site in a fasting condition, after a period of approximately 8 hours without eating, drinking (except water), or any significant physical activity and before taking study drug.
- e Visit is for tirzepatide PK blood draws
- f Medical history includes assessment of preexisting conditions (including history of gall bladder disease, cardiovascular disease, and medullary thyroid carcinoma) and substance usage (such as alcohol and tobacco).
- g Weight measurements must be in kilograms.
- h Electrocardiograms occurring on visits with tirzepatide PK collection should be collected at least 30 minutes prior to obtaining the sample for tirzepatide PK measurement.
- i Vital sign measurements should be taken before obtaining an ECG tracing and before collection of blood samples for laboratory testing, at visits where required. The participant should sit quietly for 5 minutes before vital sign measurements are taken. For each parameter, 2 measurements will be taken using the same arm; the recordings should be taken at least 1 minute apart. BP must be taken with an automated blood pressure machine.

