Patients will be instructed on how to use the single-dose pen (SDP) and will inject their first dose of study drug while in the clinic for Visit 3. The date and time of the first dose of study drug should be recorded on the electronic case report form (eCRF).

Following randomization, patients will participate in a 40-week treatment period.

Postrandomization period (end of Visit 3 to Visit 14):

The starting dose of study drug will be 2.5 mg QW for 4 weeks, followed by an increase to 5 mg QW, for the duration of the study in the 5-mg group. For the 10-mg group, the starting dose of study drug will be 2.5 mg QW for 4 weeks, then the dose will be increased by 2.5 mg every 4 weeks (2.5 mg to 5 mg to 7.5 mg to 10 mg) until the 10-mg dose is reached and maintained for the duration of the study. For the 15-mg group, the starting dose of study drug will be 2.5 mg QW for 4 weeks, then the dose will be increased by 2.5 mg every 4 weeks (2.5 mg to 5 mg to 7.5 mg to 10 mg to 12.5 mg to 15 mg) until the 15-mg dose is reached and maintained for the duration of the study. For the placebo group, patients will inject matched QW placebo for the duration of the study.

Study Period III (safety follow-up period)

Safety follow-up (Visit 801) visits:

All patients who complete the treatment period are required to complete Visit 801, a safety follow-up visit approximately 4 weeks after their last treatment visit. Patients discontinuing the study early and performing an early termination (ET) visit will also be asked to perform the safety follow-up visit, so that the safety follow-up visit will be their final visit. During the safety follow-up period, patients will not receive study drug or initiate any new antihyperglycemic therapy. In the event a patient has persistent, severe hyperglycemia, defined as any FBG values within 1 week for 2 consecutive weeks is >200 mg/dL (>11.1 mmol/L) or HbA1c $\geq 8.5\%$ (≥ 69 mmol/mol), new antihyperglycemic medication can be initiated at the discretion of the investigator as described in Section 7.4.2. If any new antihyperglycemic medication is initiated during the safety follow-up period, it will not be classified as rescue therapy. Patients are also required to return any remaining study diaries to the study site at the end of this period.

Study Procedures

Patients will perform study procedures listed in the Schedule of Activities (Section 2).

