7.4.2. Initiation of New Antihyperglycemic Medication

The introduction of new antihyperglycemic medication is expected during the study only in the following situations:

- As an antihyperglycemic intervention for severe, persistent hyperglycemia ("rescue therapy"), as defined in Section [9.2.2.2](#).
- In those patients who require permanent discontinuation of study drug, but remain in the study (Section [8.1.1](#))
- During the safety follow-up period (between Visit 14 [Week 40] or ET and Visit 801), only if the patient needs additional glycemic control as outlined in Section [5.1](#) under study Period III (safety follow-up period) discussion.

If a new antihyperglycemic medication is introduced, metformin will be the first choice of therapy unless contraindicated. Glucagon-like peptide-1 receptor agonists, DPP-4 inhibitors, and pramlintide are not allowed. Initiation of insulin as first rescue intervention for hyperglycemia should be reserved for patients with severe, persistent hyperglycemia with an average FSG ≥ 300 mg/dL (≥ 16.7 mmol/L) or in other clinical situations where the investigator believes more rapid glycemic control is warranted.

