7.8.2.1. Standards of Medical Care

Investigators and other study team members are expected to treat patients according to the nationally established standards of care for diabetes management in respective participating countries, except where that treatment would be in conflict with the protocol-provided treatment

requirements. If there are no local standards of care for diabetes, the investigators should follow current published standards of care from the American Diabetes Association and the European Association for Study of Diabetes (Davies et al. 2018) during their patients' participation in this study.

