8.2. Discontinuation from the Study

In order to minimize the amount of missing data and to enable assessment of study objectives as planned in the study protocol, every attempt will be made to keep patients in the study irrespective of the following:

- adherence to study drug,
- adherence to visit schedule,
- missing assessments,
- study drug discontinuation due to an AE,
- development of comorbidities, and
- development of clinical outcomes.

The circumstances listed above are not valid reasons for discontinuation from the study.

Patients will be discontinued in the following circumstances:

- Enrollment in any other clinical study involving an investigational product or enrollment in any other type of medical research judged not to be scientifically or medically compatible with this study
- Participation in the study needs to be stopped for medical, safety, regulatory, or other reasons consistent with applicable laws, regulations, and good clinical practice
- If a female patient becomes pregnant
- If a patient is diagnosed with T1DM
- Patient requests to be withdrawn from the study

Patients who agree to provide information relevant to any study endpoint at the end of the study are not considered to have discontinued from the study.

A patient who withdraws consent and clearly indicates that there will be no further contact of any kind with the site will be considered to have discontinued from the study.

Prior to early study discontinuation, the patient may discontinue study drug and will have end-of-study procedures (ET visit) performed as shown in the Schedule of Activities (Section 2). During the ET visit, the patient will not initiate any new glucose-lowering therapy. Visit 801 (safety follow-up visit) should be performed approximately 4 weeks after the ET visit as the final study visit.

Patients discontinuing from the study prematurely for any reason should complete adverse event and other safety follow-up per Section 2 (Schedule of Activities), Section 9.2 (Adverse Events), and Section 9.4 (Safety) of this protocol.

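### Protocol 8.1.1 and 7.8.2.4 keep patients who stop study drug for pregnancy or type 1 diabetes in the trial on replacement therapy, while 8.2 removes the same patients and bars new therapy at the ET visit

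*Protocol*

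**What the plan says.** **Stay and be treated.** Protocol 8.1.1 lists circumstances in which study drug must stop. Two of them are pregnancy ("If female patient becomes pregnant") and a T1DM diagnosis. The paragraph after the list gives the consequence for everyone: "Patients who stop the study drug permanently will receive another glucose-lowering intervention and will continue participating in the trial according to the protocol". Section 7.8.2.4 has the same rule for patients who stop permanently, again without exempting either event.

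**Leave, and start nothing new.** Protocol 8.2, on discontinuation from the study, lists the same two events ("If a female patient becomes pregnant", and T1DM). Such patients have an ET visit, with Visit 801 about 4 weeks later as the last visit. On treatment, 8.2 says: "During the ET visit, the patient will not initiate any new glucose-lowering therapy". Footnote b of the Schedule of Activities adds: "If the patient is discontinuing during an unscheduled visit, that visit should be performed as the ET visit"; it says the same of scheduled visits.

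**Follow-up.** Section 5.1 (Study Period III) says: "During the safety follow-up period, patients will not receive study drug or initiate any new antihyperglycemic therapy". The exception is persistent, severe hyperglycemia: fasting glucose above 200 mg/dL over 2 consecutive weeks, or HbA1c of at least 8.5%. Section 7.4.2 follows 5.1 for the period from Visit 14 or ET to Visit 801. Apart from rescue, its only other route to new medication is: "In those patients who require permanent discontinuation of study drug, but remain in the study". Section 7.7 carries the same limit.

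**The concern.** For these two events a site has two instructions that it cannot both follow: keep the patient in the trial and start another therapy, or take the patient out and start none unless a severe threshold is met.

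Both are situations in which glucose-lowering treatment should not wait on a reading of the protocol. Appendix 5 itself describes insulin in T1DM as needed to prevent ketosis and death. In pregnancy the 5.1 threshold is a poor guide to when treatment is needed, since it was written for rescue in a general type 2 population. What is at stake is the care of a few patients and a clear rule on their trial status.

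**Working it through.** The plan states no figure on this point, so the check sets the sections side by side.

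| Question | 8.1.1 and 7.8.2.4 | 8.2, 5.1 and 7.4.2 |
|---|---|---|
| Does the patient stay in the trial? | Yes, for any permanent stop of study drug | No; pregnancy and T1DM are named |
| New therapy when the drug stops? | Yes (8.1.1: will; 7.8.2.4: should) | Not at the ET visit (8.2); otherwise only if the patient remains in the study (7.4.2) |
| New therapy before Visit 801? | Yes; the patient continues on the normal schedule | Only above the 5.1 threshold |

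1. **Overlap.** Two events, pregnancy and T1DM, are in both lists. That alone is no error, because a patient removed from the study must also stop study drug. The conflict lies in the sentence that follows the 8.1.1 list, which has no exception.

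2. **Can the sections be ranked?** The words about remaining in the study in 7.4.2 and 7.7 suggest that 8.2 is meant to govern participation. That settles the first row of the table. But once the patient has left the study, the 7.4.2 route to new therapy after stopping drug is closed, and the bars in 8.2 and 5.1 are what remain. The most natural way to reconcile participation is therefore the one that leaves treatment least clearly authorized.

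3. **Can stopping drug and ET fall on one visit?** Yes. Pregnancy tests are scheduled at Visits 7 and 12 (Weeks 12 and 24), as well as Visit 14. Under footnote b, if the patient leaves the study at the visit where the test is positive, that visit is the ET visit. There is then no interval in which therapy could start before the bar applies.

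4. **Length of the bar, read literally.** Visit 801 is 4 weeks ±7 days after ET: 28 − 7 = 21 days to 28 + 7 = 35 days, unless the threshold is met. Take an illustrative patient with fasting glucose of 180 mg/dL and HbA1c of 8.0%: 180 is not above 200, and 8.0 is below 8.5, so neither limb is met.

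5. **Short-term insulin.** Sections 5.1 and 7.7 allow up to 14 days in certain clinical situations, with surgery, hospitalization and hyperosmolar states as examples. Even if it applied, 21 − 14 = 7 and 35 − 14 = 21, so 7 to 21 days would be left uncovered.

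6. **How many patients.** The documents give no expected number. Assuming 0.2% to 1% of those randomized: 472 × 0.002 = 0.9 and 472 × 0.01 = 4.7, or about 1 to 5 patients.

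**The case against.** The strongest reply is that this is a missing cross-reference and that no patient would go untreated. Section 8.1.1 is the general rule, 8.2 the specific one, and 8.1.1 itself refers to continuing as the protocol provides. Section 8.2 also does not count as discontinued those patients who agree to give endpoint information at the end of the study. On treatment:

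- Section 5.1 (Study Procedures) recognizes that other agents may be needed after early discontinuation of study treatment.
- Section 7.8.2.4 tells the investigator to assess the need for therapy when drug stops, with an unscheduled visit if necessary.
- Section 9.2 makes the investigator responsible for appropriate medical care.
- Section 9.2.2.12 calls for assessment for ketoacidosis whatever the glucose level and says that insulin may be required.
- Section 8.2 allows drug to stop before the patient leaves the study, so therapy could start before a separate ET visit.
- The events should be rare: T1DM is excluded at entry, and women of childbearing potential need a negative pregnancy test and, if sexually active, contraception.

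Much of this stands. A reader might infer that the protocol plans for these patients to go 21 to 35 days without treatment. The documents do not support that: it takes the strictest reading of each section and passes over the permissive text. Nor does 7.8.2.1 settle the matter by having standards of care apply "except where that treatment would be in conflict with the protocol-provided treatment" requirements. Where other protocol text directs or permits treatment, it is not clear that there is a conflict for that clause to act on.

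What does not stand is the claim that the sections already agree. None of the permissive text lifts the explicit bar in 8.2 when drug stop and ET fall at one visit, and none says that it prevails over the follow-up bar in 5.1. An investigator who treated there would be doing the right thing against the wording of 8.2.

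**Conclusion.** The inconsistency is real and is in the current protocol text. For pregnancy and T1DM, 8.1.1 and 7.8.2.4 give one answer on participation and therapy, 8.2 with 5.1 and 7.4.2 gives another, and nothing ranks them.

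Its size is modest. The 21-to-35-day interval is what a literal reading would permit. Investigators would probably treat, so it is not an expected outcome. The count of about 1 to 5 patients rests entirely on the assumed 0.2% to 1%. A reader might also look for an effect on the trial's result. There is no effect on power or the primary conclusion.

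The change should still be made: the hazard to an individual patient could be serious, and the correction costs almost nothing.

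**What to change.** 1. In 8.1.1 and 7.8.2.4, open the sentence on continuing in the trial with: *Except for patients who must leave the study under Section 8.2 (pregnancy, T1DM)*.
2. In the ET-visit text of 8.2, the follow-up paragraph of 5.1 and the third bullet of 7.4.2, add: *except that patients discontinued because of pregnancy or T1DM may start clinically indicated glucose-lowering therapy (e.g. insulin) without delay, regardless of the hyperglycemia threshold*.

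No separate exception to the metformin and insulin rules is needed. Section 7.4.2 already makes metformin first choice only where it is not contraindicated, and allows insulin first where the investigator wants faster control. Section 7.7 refers to 7.4.2 for the follow-up period and so takes up the change.

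The cost is wording in five sections, in the next amendment or a clarification letter to sites, with no new procedures, data or analyses.
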